All statistical analysis and visualization of differential methylation will be performed using Partek Genomics Suite (Partek). Raw intensity data (idat files) will be imported into Partek and normalized using the Subset-quantile Within Array Normalization (SWAN). Any probes with detection  $P > 0.05$  and probes in Y- chromosome to avoid sex-specific methylation bias will be filtered out before further analysis. To identify differentially methylated CpGs, methylation  $\beta$ -values will be converted to M-values by logit-transformation for the statistical modeling purpose. For preliminary identification of patterns in DNA methylation, unsupervised hierarchical clustering among the groups of samples will be performed. The Euclidian distance among the groups of samples will be calculated by the average linkage. In order to assess variance among samples, Principal Component Analysis (PCA) will be done. To characterize the methylation patterns, differentially methylated CpGs will be classified by enhancer, CpG island or its neighbors [2 kb regions upstream and downstream of the CpG islands (shores) or 2 kb regions upstream and downstream of the CpG island shores (shelves)] and functional promoters [within 1500 bp of a transcription start site (TSS) (TSS1500), within 200 bp of a TSS (TSS200), 5' untranslated regions (5'UTR), first exon (1stExon)], and other regions (body, 3'UTR, or intergenic). Separately, we will also analyze for DNA methylation levels of miRNAs promoter regions to investigate if miRNAs methylation appears to be altered between the groups. When we have a full sample, multiple testing corrections will be performed using the Benjamini and Hochberg False Discovery Rate (FDR with significantly differential methylation levels defined at corrected  $P < 0.05$ ). Genes corresponding to differentially methylated CpGs will be used for identification of gene networks and biological pathways using the Ingenuity Pathways Analysis. In addition, we will examine differences in methylation for candidate genes that have been previously shown to be associated with lung cancer and/or with smoking using the same methods. To understand the potential biological contribution of differentially methylated CpGs to coding gene or miRNA expression (from on-going pilot study), we will correlate between the differentially methylated CpGs (M-value) from the EPIC methylation array and matched coding gene or miRNA expression (log2 transformed intensity) from the Affymetrix Human Transcriptome array or Affymetrix GeneChip miRNA array using Spearman correlations. To determine if differences in DNA methylation are associated with cytokines levels (as measured for IL-6, IL- 10, TNF-alpha, and TNF-alpha in BAL in the current on-going study), we will select CpGs corresponding to IL-6, IL- 10, and TNF-alpha from the EPIC methylation array (targeted analysis) and correlate between methylation levels and corresponded cytokines. Correlations controlling for possible confounders (e.g., age) will be explored using multiple linear regression models. We will also explore if the correlation between methylation and cytokine levels may be mediated by gene expression of cytokines using interaction analysis.

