The 'omics' (miRNA, mRNA and metabolomics) analysis and visualization of the data will be performed in the R statistical language. Data will be log2-transformed and normalized using either quantile normalization for gene expression (miRNA and mRNA) or TIC/MSTUS normalization for metabolomics. Unsupervised clustering analysis, including PCA and hierarchical clustering will be performed to visualize natural clusters in the dataset and evaluate data quality. Multiple testing corrections using the Benjamini and Hochberg False Discovery Rate (FDR) will be performed. Significantly altered genes and metabolites will be defined as those with FDR corrected p-value < 0.05 and fold changes > 2 or > 1.5, respectively. Identified genes or metabolites will be used to identify relevant networks and pathways using Ingenuity Pathways Analysis. For gene expression, we will further study associations between miRNA-mRNA pairs based on publically available target prediction databases such as TargetScanHuman, miRDB, miRWalk2.0 and others. Global integrative analysis, through correlations, will be performed using Partek software.

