For methylation, raw intensity data (idat files) will be normalized using the Subset-quantile Within Array Normalization (SWAN). Any probes with detection P > 0.05 and probes in Y-chromosome to avoid sex-specific methylation bias will be filtered out before further analysis. To identify differentially methylated CpGs, methylation β -values will be converted to M-values by logit-transformation for the statistical modeling purpose. For preliminary identification of patterns in DNA methylation, unsupervised hierarchical clustering among the groups of samples will be performed. The Euclidian distance among the groups of samples will be calculated by the average linkage. In order to assess variance among samples, Principal Component Analysis (PCA) will be done. To characterize the methylation patterns, differentially methylated CpGs will be classified by enhancer, CpG island or its neighbors [2 kb regions upstream and downstream of the CpG islands (shores) or 2 kb regions upstream and downstream of the CpG island shores (shelves)] and functional promoters [within 1500 bp of a transcription start site (TSS) (TSS1500), within 200 bp of a TSS (TSS200), 5' untranslated regions (5'UTR), first exon (1stExon)], and other regions (body, 3'UTR, or intergenic). Separately, we will also analyze for DNA methylation levels of miRNAs promoter regions to investigate if miRNAs methylation appears to be altered between the groups. When we have a full sample, multiple testing corrections will be performed using the Benjamini and Hochberg False Discovery Rate (FDR) with significantly differential methylation levels defined at corrected P < 0.05. Genes corresponding to differentially methylated CpGs will be used for gene networks and biological pathways using the Ingenuity Pathways Analysis. In addition, we will examine differences in methylation for candidate genes that have been previously shown to be associated with lung cancer and/or with smoking using the same methods. To understand the potential biological contribution of differentially methylated CpGs to coding gene or miRNA expression (from on-going pilot study), we will correlate between the differentially methylated CpGs (M-value) from the EPIC methylation array and matched coding gene or miRNA expression (log2 transformed intensity) from the Affymetrix Human Transcriptome array or Affymetrix GeneChip miRNA array using Spearman correlations. To determine if differences in DNA methylation are associated with cytokines levels (as measured for IL-6, IL- 10, TNF-alpha, and TNF-alpha in BAL in the current on-going study), we will select CpGs corresponding to IL-6, IL- 10, and TNF-alpha from the EPIC methylation array (targeted analysis) and correlate between

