- 4) For mtDNA features, Model 1 is also used. CN is expected to be Gaussian, while mutation rate is expected to be low counts; therefore, a t-test was powered for CN and Poisson [3] for mutation rate. Because there will only be several comparisons here, the significance threshold used for power corresponds to one expected false discovery per 100 tests. We believe that this threshold is a good balance between potential Type I and Type II errors, given the number of tests. The coefficient of variation was calculated from results in the

literature, as cited in the main body of the protocol. For CN, with 21 samples per group, considering a significance threshold of 0.01, a two-sided, two-sample t-test achieves 80% power to detect an 1.4 fold difference between arms considering a coefficient of variation of 0.32 [4]. For mutation, Poisson regression achieves 80% power to detect a mutation rate ratio of 2.7 between arms considering a significance threshold of 0.01 and 21 samples per group [5].

- 5) For associations between mtDNA and other 'omics features, we assume the regression model [6]:

$$\text{Followup_Expression} = \text{Baseline_expression} + \text{arm} + \Delta\text{mtDNA feature} + e,$$

Where $\Delta\text{mtDNA} = \text{Followup_mtDNA} - \text{Baseline_mtDNA}$. We consider this model across all arms. The effect of arm is included as a covariable to ensure that associations are not simply due to both features being associated with arm; rather, we are looking for a more direct relationship. Again, we consider a significance threshold corresponding to one expected false discovery per 10,000 tests, as described above. To generalize, we assume unit standard deviations of the dependent and independent variables (each feature will have a different standard deviation, so results are calculated in terms of standard deviations). With 84 samples, considering a significance threshold of $p=0.0001$ and unit standard deviations for dependent variable residuals and ΔmtDNA features, linear regression achieves 80% power to detect a slope of 0.48.

- 6) For comparing mtDNA features between nasal and bronchial samples, mixed Poisson or mixed Gaussian will be employed with a random effect for subject, and a main effect for location (bronch vs. nasal):

$$\text{Feature} = \text{sample\&rand} + \text{location} + e.$$

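### CpGs selected for differing between groups are correlated with expression without a group term, so a CpG and a gene that both shift with arm can appear linked

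*SAP*

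**What the plan says.** **Selection.** In the methylation paragraph of SAP item 2, the CpGs of interest are those with "significantly differential methylation levels defined at corrected P < 0.05", after Benjamini-Hochberg correction. The context makes this a comparison between groups.

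**Correlation with expression.** For those CpGs, "we will correlate between the differentially methylated CpGs (M-value) from the EPIC methylation array and matched coding gene or miRNA expression". The Protocol (4.g.i, Data Analysis Plan) describes the same step, also "using Spearman correlations". The stated aim is to learn what the selected CpGs may contribute biologically to gene or miRNA expression. Neither document gives the time point, a significance level, or whether arms are pooled. The expression data are described as "from on-going pilot study", yet also as matched to the methylation data.

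**Correlation with cytokines.** The CpGs here are those belonging to IL-6, IL-10 and TNF-alpha. They are picked by gene, not by a difference between arms. No arm term is named.

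**Adjustment.** After the cytokine step, item 2 says that correlations adjusted for possible confounders will be explored by multiple linear regression. Age is the only example given.

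**Elsewhere in the SAP.** Item 5 relates changes in mitochondrial DNA to other 'omics features and says: "The effect of arm is included as a covariable to ensure that associations are not simply due to both features being associated with arm".

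**The concern.** Arm is a possible common cause of both features. Continued smoking against switching may move a CpG, and it may separately move a gene. Pooling the arms then produces a correlation that reflects only the two arm differences. The expression step is especially exposed because its CpGs enter the analysis for differing between groups, so half of the condition is met by design.

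The aim of the step is mechanistic. A pooled correlation cannot separate a CpG that tracks expression from person to person from a CpG and a gene that respond separately to the same exposure. At stake is which CpG-gene pairs are reported as biologically linked. The SAP accepts this argument in item 5 and does not apply it in item 2.

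**Working it through.** The documents state no power, sample size or error rate for these correlations, so there is no figure of the plan's to reproduce.

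**Inputs from the documents**
- Completers: 21 per arm, 84 in total (SAP item 1).
- Scale for an expression shift: 2.1-fold at CV 0.5 (SAP item 3). On the log scale the SD is sqrt(ln(1 + 0.5²)) = sqrt(0.2231) = 0.472, and ln(2.1) = 0.742, so the shift is 0.742 / 0.472 = 1.57 SD.
- Stringent threshold: 0.0001 (SAP item 3).

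**Assumptions**
- A two-sided level of 0.05, because none is given; 0.0001 is shown as the other end.
- Samples pooled across arms at follow-up.
- Normal features with no association within any arm.
- Shifts of 0.5 to 1.57 SD. The documents give no methylation effect size, so this is a range and not an estimate.

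**Formula.** If both features shift by d SD along an arm pattern with variance v, the pooled Pearson correlation is d²v / (1 + d²v). For control against the other three arms, v = 0.75 × 0.25 = 0.1875.
- d = 0.5: 0.047 / 1.047 = 0.045
- d = 1: 0.1875 / 1.1875 = 0.158
- d = 1.57: 0.4625 / 1.4625 = 0.316

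**Simulation.** Rejection rate of the pooled Spearman test at 0.05, from repeated runs of 2,000 to 10,000 replicates. Where runs differed, the range is shown. Graded means shifts of 0, 0.5, 0.75 and 1 times d.

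| Shift in both features | 4 arms, control vs other three | 4 arms, graded | 2 arms (42 subjects) |
|---|---|---|---|
| 0.5 SD | 6–8% | 5–6% | 6–7% |
| 0.8 SD | 14–15% | 10% | 13–14% |
| 1.0 SD | 28–29% | 18–19% | 25–26% |
| 1.5 SD | 76–78% | 57% | 72% |
| 1.57 SD | 81–84% | 64–65% | 78–80% |

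Further results for four arms, control against the other three:
- At 0.0001, the rate is 12% for 1.57 SD and below 1% for 1 SD.
- If only one feature shifts by 1.57 SD, the rate at 0.05 is 5%. This includes an unshifted cytokine-gene CpG against a shifted cytokine.
- If the CpG has no true shift but was selected at an unadjusted p < 0.05 between arms, and expression shifts by 1.57 SD, the rate is 13%. With arm adjustment it is 4%.

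**With arm in the analysis.** Centring the ranks within arm leaves 84 − 4 − 1 = 79 degrees of freedom, against 82 unadjusted. The rejection rate at 0.05 is then 4% to 6.5% in every scenario, and the mean adjusted correlation is about zero.

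**The case against.** **Pooling and data source are not stated.** This stands. SAP item 3 compares arms pairwise, and these correlations might be too. The two-arm column shows that this does not remove the problem; only a within-arm analysis would. The pilot wording is a real ambiguity: the Protocol's Specific Aims describe cross-sectional preliminary data on smokers, non-smokers and e-cigarette users. If those data are meant, there is no trial arm. The same distortion would then come from the pilot's groups, and the simulated figures would not apply as they stand.

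**The large rates need large shifts in both features.** This also stands. The Protocol's background notes that some smoking-related methylation changes do not reverse even decades after quitting, so large shifts after 8 weeks cannot be assumed. Below about 0.8 SD the inflation is modest.

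**The exploratory regression could include arm.** Its list is open, but arm is not named. The sentence follows the cytokine step and may not cover the expression step. The SAP's metabolite model does contain a treatment term, but it relates miRNA, genes or cytokines to metabolites, not methylation.

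**Adjusting for arm discards treatment-induced variation.** It does, and some of that variation may be real mediation. But a CpG that influences expression should also do so among people in the same arm. The between-arm part alone cannot tell mediation from two parallel responses.

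**Stronger readings that the text does not support.** A reader might infer that the cytokine CpGs are also selected for differing between arms; they are selected by gene. A reader might infer that the declared links will be spurious; the text supports only that they can be, under the conditions above. A reader might extend the point to the planned global correlations in Partek. That step involves no selection of CpGs, its paragraph covers miRNA, mRNA and metabolomics, and the point does not need it.

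**Conclusion.** The point holds for the CpG-expression correlations, conditionally. If samples are pooled across arms and both features shift with arm, an unadjusted Spearman correlation can declare a link where none exists within any arm. At 0.05 the error is slight for 0.5 SD shifts, more than five times nominal at 1 SD (28/5 = 5.6) and above 80% at 1.57 SD when the other three arms shift equally. Graded shifts or a 0.0001 threshold lower these rates. No inflation appears if only one feature has a real shift, apart from the modest effect of selecting the CpG on the same samples.

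For the CpG-cytokine correlations the same term is missing, but the exposure is smaller: those CpGs are not selected on arm, and distortion requires both CpG and cytokine to shift.

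The between-arm comparisons of SAP item 3 do not depend on this step. It is a change that should be made to a downstream analysis, and it rests on a principle the SAP already states in item 5.

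**What to change.** In SAP item 2, and in the matching Protocol text:

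1. Test each CpG-expression pair by a partial Spearman correlation adjusted for arm, or by a linear model with arm as a covariable. Give the reason already used in item 5.
2. State whether the expression data come from trial participants or the pilot. If from the pilot, adjust for the pilot's group variable instead of arm.
3. State the time point of the samples and the significance rule.
4. Keep the unadjusted Spearman correlation as a descriptive result only.
5. Add the same arm term to the IL-6, IL-10 and TNF-alpha CpG-cytokine correlations, noting that these CpGs are chosen by gene and that the term matters only if CpG and cytokine both shift with arm.

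The cost is a few sentences and about 3 degrees of freedom with four arms; no new data are needed. Fewer correlations will be declared, and associations carried only by the between-arm difference will no longer count as evidence of a direct link.

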**The Effects of a Standardized Research E-Cigarette on the Human Lung:
A Clinical Trial with Bronchoscopic Biomarkers**

NCT03691350

Statistical Analysis Plan, 09/19/22

SREC SAP

The Specific Aim for this two year project is:

To assess inflammatory changes over 10 weeks (8 weeks experimental condition) for lung and urine biomarkers in smokers in a clinical trial where smokers are randomized to: continued use (n=32), complete switching to the nicotine standardized research electronic cigarette (SREC) (n=32), complete switching to the placebo SREC (n=32), or complete switching to nicotine replacement therapy (NRT) (n=32).

- 1) We will enroll 128 subjects (32 per group). For power calculations, we will use a conservatively planned 66% retention rate at 5 weeks, knowing that we have a 100% retention for never smokers receiving serial bronchoscopies. Thus, the final sample size will be 21 subjects per group (n=84). Although we expect a higher retention rate, we assume 66% to ensure that we have the minimal numbers required to reach meaningful conclusions. Since follow-up samples would not be obtained from subjects that do not finish the treatment protocol, and these samples (inflammation/omics) are our primary outcomes, we cannot use an 'intent to treat' strategy since dropouts will have missing outcome data for any analyses including follow-up measurements (the primary Aim). In light of this, we will compare dropout rates between arms and with demographic/clinical to ensure that the analyses results are not biased by unbalanced dropouts. We will also test for differences in baseline molecular measurements between subjects that dropout after baseline samples are taken vs. subjects that complete the protocol. While we will make every effort to minimize the missing data for this study, missing data can arise due to various reasons. Violation of missing completely at random (MCAR) will be checked by evaluating whether any covariates are associated with missing data. If so, these covariates will be subsequently included and controlled for in the GL(M)M models. In addition, sensitivity analyses will also be conducted using results from multiple imputation.

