Understanding the epigenomic/genomic/proteomic/environment context and regulation of metabolic phenotypes will expand our knowledge of the effects of e-cig on lung biology, and could contribute to finding successful interventions, including accurate predictions of e-cig related adverse effects. Typical omics integration methods include logistic regression or correlations among omics measurements (when measured in the same samples), intersection of gene/protein/metabolite lists (when measured in different samples), or further downstream integration by assessing alterations in pathways. Because our omics measurements will be made in the same sample, we will be able to directly assess relationships between our molecular data through regression or correlation analyses. Of note, typical regression/correlation approaches are not appropriate for low sample numbers, and they do not readily adjust for differences in sample size between phenotype groups or for potential confounders. Another approach, which we propose here, is to directly test whether associations between miRNA or gene or cytokine and metabolite levels are specific to a group assignment. To test this, we will apply a novel linear model approach recently developed by [name] for these types of analysis: $m = g + t + g:t$, where m are metabolite abundances, g are miRNA or gene or cytokine levels, t is treatment group (e.g., SREC vs. continued smoking), and g:t is the interaction between miRNA or gene or cytokine level and treatment group. A statistically significant g:t interaction p-value would indicate that gene (or miRNA or cytokine):metabolite relationships are present in one treatment group and not the

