
methylation levels and corresponded cytokines. Correlations controlling for possible confounders (e.g., age) will be explored using multiple linear regression models. We will also explore if the correlation between methylation and cytokine levels may be mediated by gene expression of cytokines using interaction analysis.

- 3) To compare treatment groups at follow-up for inflammatory markers and 'omics data, we will use generalized linear models (pairwise) with a covariable for baseline measure to account for baseline differences:

$$\text{Model 1: Followup_Measure} = \text{Baseline_Measure} + \text{arm} + e.$$

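### The exploratory question of mediation by cytokine gene expression is paired with an interaction test, which assesses effect modification and not mediation

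*SAP*

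**What the plan says.** The methylation part of SAP item 2 ends with a plan to explore whether the correlation between methylation and cytokine levels "may be mediated by gene expression of cytokines using interaction analysis". Protocol section 4.g.i (Data Analysis Plan) has the same sentence. Neither document adds a model, an indirect effect, an interval or a decision rule.

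The SAP does explain what it means by an interaction in other places. In the multi-omics model of item 2, "g:t is the interaction between miRNA or gene or cytokine level and treatment group", and a significant term is read as showing that the "relationships are present in one treatment group and not the" other. Item 7 uses an arm-by-origin product term to ask whether treatment is associated with differences between tissues. Both are questions of effect modification, and both are matched correctly to their method.

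Two neighbouring analyses cover parts of the pathway. Differentially methylated CpGs are related to gene or miRNA expression from the Affymetrix Human Transcriptome array or the "Affymetrix GeneChip miRNA array using Spearman correlations". CpGs for the three cytokine genes are correlated with cytokine levels, and "Correlations controlling for possible confounders (e.g., age) will be explored using multiple linear regression models".

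**The concern.** Mediation asks whether expression lies on the path from methylation to cytokine level. An interaction asks whether the methylation–cytokine slope changes with the level of expression. A linear mediator need produce no interaction, and an interaction can exist when methylation has no effect on expression at all.

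If the sentence is carried out as the SAP uses the word elsewhere, a null product term could be read as no mediation and a significant one as mediation. Neither inference is valid. What is at stake is the interpretation of one exploratory pathway analysis, not a treatment comparison.

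**Working it through.** The plan states no power, alpha, effect size or sample size for this analysis, so there is no figure to reproduce. The check is on the logic, with a simulation to show its size.

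**Model.** Let X be methylation, M expression and Y cytokine level:

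- M = aX + e₁
- Y = cX + bM + dXM + e₂

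With d = 0, the effect of X on Y through M is a × b. The product-term test addresses d = 0. Mediation requires both a and b to be non-zero. If d = 0 and ab ≠ 0, the null hypothesis of the interaction test is true, so it rejects at alpha however strong the mediation is. If a = 0, X does not move M, so there is no mediation whatever the value of d.

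**Do the neighbouring analyses fill the gap?** The Spearman step addresses a, but only for differentially methylated CpGs. The regression step addresses the total association of X with Y; expression is not named as a covariable. No stated analysis estimates b (cytokine on expression given methylation) or compares the methylation coefficient with and without expression.

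**Inputs.**

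- n = 84: the expected completers in all arms (SAP item 1, 21 per group; 4 × 21 = 84).
- n = 42: two arms (2 × 21). That either n applies here is an assumption.
- Alpha 0.05 two-sided, and paths of 0.5 or 0.3 or an interaction of 0.5 in standardised units: all assumed.

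**Tests.** (i) The XM term in the regression of Y on X, M and XM. (ii) Joint significance: a in M on X, and b in Y on X and M, both significant. There were 4,000 simulated datasets per scenario. The ranges reflect simulation error and whether M is scaled to unit total variance or to unit residual variance.

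| Scenario | n | Interaction test rejects | Joint-significance test rejects |
|---|---|---|---|
| Mediation only, a = b = 0.5, c = d = 0 | 84 | about 5% | 96–98% |
| | 42 | about 5% | 70–73% |
| Mediation only, a = b = 0.3, c = d = 0 | 84 | about 5% | about 57% |
| | 42 | about 5% | about 20% |
| Interaction only, a = b = 0, c = d = 0.5 | 84 | 97–98% | about 0.5% |
| | 42 | 76–78% | about 0.5% |

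Two variants mark the limits. With both mediation and interaction (a = b = 0.5, c = 0, d = 0.3, n = 84, unit total variance), the interaction test rejects in about 79%, but because of d and not because of ab. With a = 0, b = 0.5 and c = d = 0.5 at n = 84, the interaction test rejects in about 98% and the joint test in about 5%, although there is again no mediation.

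**The case against.** The strongest reply is that the sentence is under-specified rather than wrong. No model is given, and the authors may have had in mind a mediation model that allows an exposure–mediator interaction. Or *mediated* may be loose wording for *modified*, in which case the method is right and one word changes. The second possibility stands, and the fix must allow for it. The first is not supported: no mediator model or indirect effect is stated, and the SAP's own usage points to a product term. Where item 5 wants to separate a direct relationship from a shared dependence on arm, it uses covariate adjustment, so interaction is not the SAP's word for adjustment either.

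The simulation is also partly built in. Setting d to zero guarantees rejection at about alpha, and the path sizes come from no document. That is fair. The table illustrates the mismatch and does not forecast this trial's results. The adjacent sentences also refer to data from ongoing studies, so even the dataset is uncertain.

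A reader might infer that real mediation would always be missed. The documents do not support that. It holds only when methylation and expression do not interact; when they do, the test may well reject, though the rejection is still not evidence of mediation. A reader might also infer that the trial's main conclusions are exposed. They are not: the sentence is worded as exploration, concerns CpGs for three cytokine genes, and feeds neither the arm comparisons nor the sample size.

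**Conclusion.** The concern holds in this limited form. Both documents set a mediation question and name a method that, on the SAP's own usage, tests effect modification. For mediation without interaction, the named test has no power beyond its false-positive rate, whatever the sample size or path strength. That part is a matter of logic. The power of a proper mediation test does depend on assumptions: from 96–98% (paths 0.5, n=84) down to about 20% (paths 0.3, n=42).

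Exploratory status excuses low power or loose error control. It does not make a test of one hypothesis answer another. The importance is modest because the analysis is peripheral, but the correction is nearly free and should be made.

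**What to change.** Change the sentence in both SAP item 2 and Protocol section 4.g.i, according to what was meant.

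- **If mediation is the question:** replace the reference to interaction analysis with two regressions, expression on methylation, and cytokine on methylation plus expression. Use the same confounders in both, and include arm where follow-up data are used. Report the indirect effect with a bootstrap confidence interval. Label it hypothesis-generating, because methylation is not randomised and all three quantities are measured at the same visits (Protocol Table 3). Label any interaction test separately as moderation.
- **If effect modification is the question:** change *mediated* to *modified*, keep the interaction test, and do not report the result as mediation.

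In either case, state which visit's data, and so what n, the analysis uses. The cost is one sentence in each document and a few lines of code, with no new data.
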